7.2.7 Interim Analyses

No interim analysis is planned, but a SMC will be in place with tasks as described in [Section 8.7](#).

Furthermore, the study will include two database locks (DBL 1 and DBL 2). The first DBL will be announced once 30 patients (at least 20 adolescents aged 12-17 years, and if feasible at least 10 children aged 6-11 years) have completed PK sampling at 26 weeks, or prematurely discontinued the trial (last-patient-last-visit-primary-endpoint). At this timepoint patient recruitment will close. Based on the data from DBL 1 (or updated DBL 1 data once the number of patients with sufficient PK data has been reached), the primary analysis and a benefit-risk assessment will be done and the clinical trial report for the primary analysis will

be written. If PK data collected for the primary analysis are not sufficient, then further PK data will be collected as explained in [Section 3.1](#).

The timing of final DBL (DBL 2) and EoT visit will be communicated after confirming adequacy of PK data from DBL 1 (or updated DBL 1 data). Please see [Section 3.1](#) for further details.

Moreover, the primary analysis may be conducted while the data collection for selected other analyses is still ongoing.

7.3 HANDLING OF MISSING DATA

In general, missing data will not be imputed.

Missing or incomplete AE onset and end dates are imputed according to BI standards.

The mixed effect model will handle missing data based on a likelihood method under the "missing at random assumption".

In the analysis of time-to-event endpoints, missing or incomplete data will be handled using standard survival analysis techniques (i.e. censoring).

In the analyses of the binary endpoints, multiple imputation will be used to handle missing data at week 24. For week 52 and later, data will not be imputed and only observed values will be used.

For pharmacokinetics:

Handling of missing PK data will be performed according to BI standards. For the non-compartmental analysis, concentration data identified with NOS (no sample), NOR (no valid result), NOA (not analysed) will generally not be considered. Concentration values in the lag phase identified as BLQ or NOP will be set to zero. All other BLQ (below the limit of quantification), and NOP (no peak detectable) values of the profile will be ignored. The lag phase is defined as the period between time zero and the first time point with a concentration above the quantification limit.

7.4 RANDOMISATION

Patients will be randomised to each treatment group with an approximate ratio of 2:1 (nintedanib:placebo) stratified by age group (6 - <12 years; 12 - <18 years). BI will arrange for the randomisation and the packaging and labelling of trial medication. The randomisation list will be generated using a validated system, which involves a pseudo-random number generator so that the resulting treatment will be both reproducible and non-predictable. The block size will be documented in the CTR. Access to the codes will be controlled and documented.

7.5 DETERMINATION OF SAMPLE SIZE

For the primary evaluation of PK including the assessment on whether nintedanib exposure at steady-state ($AUC_{\tau,ss}$) in paediatric patients is comparable to adult exposure, the clearance

parameter needs to be estimated with adequate precision. Assuming a coefficient of variation (CV) of 70.8% (based on geometric CV [gCV] of apparent clearance at steady-state [CL/F_{ss}] after extravascular administration observed in the PK meta-analysis [[U11-1639-01](#)]), at least 20 actively treated patients with available PK measurements per age group (6 - <12 years; 12 - <18 years) would be needed to achieve at least 80% probability (loosely referred to as power in this context [[R12-0884](#)]) of having the 95% CI of nintedanib CL/F_{ss} and with this AUC_{τ,ss} within 60% and 140% of the geometric mean estimate. This calculation was performed as described by Wang et al. [[R12-0884](#)] using R Version 3.5.1.

[Table 7.5: 1](#) provides an overview of the achievable probability of having the 95% CI of nintedanib CL/F_{ss} and with this AUC_{τ,ss} within 60% and 140% of the geometric mean estimate.

Table 7.5: 1 Probability that can be expected of having the 95% CI of nintedanib CL/F_{ss} and with this AUC_{τ,ss} within 60% and 140% of the geometric mean estimate.

| gCV [%] | Sample Size | Probability [%] |
|---------|-------------|-----------------|
| 60 | 16 | 80.60 |
| 60 | 18 | 91.20 |
| 60 | 20 | 96.82 |
| 60 | 22 | 99.10 |
| 60 | 24 | 99.81 |
| 70.8 | 16 | 52.82 |
| 70.8 | 18 | 68.03 |
| 70.8 | 20 | 81.03 |
| 70.8 | 22 | 90.32 |
| 70.8 | 24 | 95.82 |
| 80 | 16 | 32.78 |
| 80 | 18 | 45.71 |
| 80 | 20 | 59.64 |
| 80 | 22 | 72.81 |
| 80 | 24 | 83.63 |

Based on the inclusion criteria of the proposed study and preliminary feasibility assessment, it is anticipated that the study will only be powered for patients with ≥ 12 years of age. PK parameters in children < 12 years will be collected and analysed but are expected to be limited due to expected small number of patients falling in that age range.

To further optimise PK assessment from the study population, on-treatment PK sampling is planned in those assigned to placebo after switching to active treatment. By this, 30 randomized paediatric patients have the possibility to contribute for the PK assessment at the time of primary analysis. This increases the sample size for the PK analysis.

The target sample size of a minimum of 30 patients is based on the sample size estimation for the evaluation of the primary endpoint of PK and trial feasibility evaluation. Although the planned basket approach makes it feasible to evaluate this extremely rare patient population, one of the limitations of this approach is the heterogeneity of the study populations, especially in evaluating efficacy outcomes of potential interest (e.g. lung function). Due to the high unmet medical need, lack of therapeutic options and the potential for more robust efficacy evaluation, patient recruitment into the treatment phase will remain open until 30 patients (at least 20 adolescents aged 12-17 years, and if feasible at least 10 children aged 6-11 years) have completed PK sampling at 26 weeks, or prematurely discontinued the trial. This will allow for any eligible patient identified beyond the target (i.e. 30 subjects randomized including at least 20 adolescents aged 12-17 years) to have access to study drug. Although the duration of the blinded treatment period (Part A) will be variable in some of these patients, all PK and clinical data collected will be used in the primary analysis to allow for more robust estimate of exposure and potential treatment effect.

8. INFORMED CONSENT, TRIAL RECORDS, DATA PROTECTION, PUBLICATION POLICY, AND ADMINISTRATIVE STRUCTURE

The trial will be carried out in compliance with the protocol, the ethical principles laid down in the Declaration of Helsinki, in accordance with the ICH Harmonized Guideline for Good Clinical Practice (GCP), relevant BI Standard Operating Procedures (SOPs), the EU directive 2001/20/EC / EU regulation 536/2014 and other relevant regulations. Investigators and site staff must adhere to these principles. Deviation from the protocol, the principles of ICH GCP or applicable regulations as will be treated as “protocol deviation”.

Standard medical care (prophylactic, diagnostic and therapeutic procedures) remains the responsibility of the treating physician of the patient.

The investigator will inform the sponsor immediately of any urgent safety measures taken to protect the trial patients against any immediate hazard, as well as of any serious breaches of the protocol or of ICH GCP.

The Boehringer Ingelheim transparency and publication policy can be found on the following web page: trials.boehringer-ingelheim.com. The rights of the investigator and of the sponsor with regard to publication of the results of this trial are described in the investigator contract. As a rule, no trial results should be published prior to finalisation of the Clinical Trial Report.

The certificate of insurance cover is made available to the investigator and the patients, and is stored in the ISF.

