2.1.2 Primary endpoints

Primary endpoints:

[figure not shown]
- PK: AUC_{τ,ss} based on sampling at steady state (at week 2 and week 26);
- N (%) of patients with treatment-emergent adverse events at week 24.

[figure not shown]

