7.2.2 Primary endpoint analyses

For the primary PK analysis, the area under the plasma concentration-time curve at steady state ($AUC_{\tau,ss}$) will be calculated by non-compartmental as well as compartmental analysis and descriptive statistics will be provided as detailed in [Section 7.2.1](#).

For patients receiving nintedanib in Part A, PK profiles on week 2 and week 26 are planned to be collected. For the primary endpoint $AUC_{\tau,ss}$ the $AUC_{\tau,ss}$ at week 2 will be used. If the week 2 value is missing, then it will be replaced by available $AUC_{\tau,ss}$ at week 26. For patients receiving placebo in Part A and nintedanib in Part B, $AUC_{\tau,ss}$ evaluated based on PK profiles at week 26 will be used (which corresponds to week 2 on active treatment). Further details on the PK analysis will be specified in the TSAP.

The primary safety endpoint listed in [Section 2.1.2](#) will be derived according to BI standards. For the primary analysis, only treatment emergent AEs during the double-blind period until week 24 will be included. The analysis will be based on the TS and will be descriptive in nature.

Subgroup analyses will be specified in the TSAP.

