5.1 PRIMARY ENDPOINT(S)

The primary PK endpoint is the $AUC_{\tau,ss}$ based on sampling at steady state (at week 2 and week 26 visit).

For patients receiving nintedanib in Part A, PK profiles on week 2 and week 26 are planned to be collected. For the primary endpoint $AUC_{\tau,ss}$ the $AUC_{\tau,ss}$ at week 2 will be used. If the week 2 value is missing, then it will be replaced by available $AUC_{\tau,ss}$ at week 26 (or later, if PK visit was postponed). For patients receiving placebo in Part A and nintedanib in Part B, $AUC_{\tau,ss}$ evaluated based on

PK profiles at week 26 (or later, if PK visit was postponed) will be used (which corresponds to week 2 on active treatment).

The primary safety endpoint is the N (%) of patients with treatment-emergent adverse events at week 24, i.e., during the planned double-blind period of the trial.

Thus, the number of patients experiencing at least one adverse event during the double-blind period of the trial will be analyzed, see [Section 7.8](#).

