6.3 SUBJECT SETS ANALYZED

The following analysis sets are defined for this trial:

- **Screened set (SCS):**
This patient set includes all patients having signed informed consent.
- **Randomised set: (RS)**
This patient set includes all randomised patients, whether treated or not.
- **Treated Set (TS):**
The Treated Set (TS) consists of patients who are randomized to a treatment group and receive at least one dose of study medication.
- **Pharmacokinetic parameter analysis set (PKS):**
This set includes all patients in the treated set (TS) who provide at least one PK endpoint that was not excluded due to a protocol deviation relevant to the evaluation of PK or due to PK non-evaluability (as specified in the CTP Sec. 7.2.1.). Thus, a patient will be included in the PKS, even if he/she contributes only one PK parameter value for one period to the statistical assessment. Descriptive and model based analyses of PK parameters will be based on the PKS.

Analyses for PK endpoints will be based on the PKS. All other analyses will be based on the TS except for disposition.

Table 6.3: 1 Patient sets analyzed

Class of endpoint	Patient set		
	SCS	TS	PKS
Primary endpoint PK			X
Primary endpoint Safety		X	
Secondary endpoints		X	
Further endpoints Efficacy		X	
Further endpoints PK			X
Safety endpoints		X	
Demographic/baseline characteristics		X	
Disposition	X		

Note that the number of patients with available data for an endpoint may differ. For details, see [Section 6.6](#)

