7. PLANNED ANALYSIS

Unless otherwise specified, all analyses described in this section will be done on the Treated Set. The labelling and display format of statistical parameters will follow BI standards ([10](#)). For End-Of-Text (EoT) tables, the set of summary statistics is: N / Mean / SD / Min / Median / Max.

In descriptive statistics tables, mean, SD and median will be rounded to one additional digit than the raw individual value. In case some endpoints show some extreme data outside the expected range, quartiles and percentiles will be presented additionally.

Tabulations of frequencies for categorical data will include all possible categories and will display the number of observations in a category as well as the percentage (%) relative to the respective treatment group (unless otherwise specified, all patient in the respective subject set whether they have non-missing values or not). The precision for percentages should be one decimal point. The category missing will be displayed only if there are actually missing values.

Unless otherwise specified, all analyses will be provided by randomized treatment group (placebo or nintedanib) and overall (total).

[figure not shown]
For efficacy and safety end point analyses by time point, as well as for the safety analyses of Part A, patients switching during Part A to Part B will be censored at the time point of the switch and for the safety analyses of Part A (due to the definition of the double-blind period). Patients who started directly in Part B will be analyzed as a separate cohort, in addition to those randomized to nintedanib and those randomized to placebo.

[figure not shown]
All analyses performed after DBL1 will be repeated after DBL2 to include newly emerging data.

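### The crude week-24 AE percentage counts event-free late entrants with a shortened Part A as full non-events, so read as a 24-week risk it is somewhat low in both arms

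*Protocol*

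**What the plan says.** Protocol 2.1.2 gives the endpoint as "N (%) of patients with treatment-emergent adverse events at week 24", and Protocol 7.2.2 adds that "only treatment emergent AEs during the double-blind period until week 24 will be included". SAP 5.1 keeps the label but makes it operational as a period: "the number of patients experiencing at least one adverse event during the double-blind period of the trial will be analyzed". SAP 7.4.1.2 presents it as counts and frequencies by SOC and PT, referring to SAP 7.8.1.

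The denominator is set in two places. Under SAP 7, percentages are taken over "all patient in the respective subject set whether they have non-missing values or not". Under SAP 6.3, "The Treated Set (TS) consists of patients who are randomized to a treatment group and receive at least one dose of study medication"; no minimum follow-up is required.

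Part A can end before 24 weeks for late entrants. Protocol 3.1 closes recruitment only when 30 patients have reached the week-26 PK visit or stopped early. A patient still in Part A may then be cut off by DBL 1, sent to an EoT visit once the PK data are judged adequate (late entrants are expressly included) or, in what the protocol calls a rare case, moved to Part B. Protocol 7.5 accepts this: "Although the duration of the blinded treatment period (Part A) will be variable in some of these patients", all their data are used. For the last route SAP 7 adds that "patients switching during Part A to Part B will be censored at the time point of the switch".

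**The concern.** A percentage has a numerator and a denominator but no time axis. A late entrant who has been blinded for three weeks without an AE adds one to the denominator and nothing to the numerator, exactly like a patient followed for 24 weeks without one. The instruction to censor at the switch cannot change that, because a crude proportion has no means of censoring.

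This matters because the figure carries a week-24 label and is one of two primary endpoints. A reader will take it as the probability of a treatment-emergent AE within 24 weeks. On that reading it is too low, by an amount that depends on how many patients happen to enter late and not on the drug.

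**Working it through.** **No stated figure to reproduce for this endpoint.** The documents give no expected AE rate or precision for it. The numerical result in Protocol 7.5 concerns PK: 81.03% at gCV 70.8% and n = 20. It recomputes to 81.03% but is not an input here.

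**Number of late entrants.** Protocol 3.2 assumes 18 months (78 weeks) to recruit 30: 30/78 = 0.385 per week. If that pace continued for the 26 weeks after the thirtieth patient, 0.385 × 26 = 10 more would enter, of whom 0.385 × 24 = 9.2 would have under 24 weeks at the trigger. The documents plan no number, so I bracket the late share f between 3 of 33 (9%) and 10 of 40 (25%).

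**Formula.** Let p be the true 24-week risk, and let late patients have Part A follow-up spread uniformly over 0 to 24 weeks, with mean risk m. Then

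crude % = (1 − f)·p + f·m.

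- Constant hazard: m = 1 − p/(−ln(1 − p)). For p = 0.80, m = 1 − 0.80/1.609 = 0.503.
- All risk in the first 12 weeks: m = (0.503 + 0.80)/2 = 0.651, because half of the late patients have already passed week 12.

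Example at f = 0.25, constant hazard: 0.75 × 0.80 + 0.25 × 0.503 = 0.726, a shortfall of 7.4 points.

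| True risk | Constant, 3/33 | Constant, 10/40 | First 12 weeks, 3/33 | First 12 weeks, 10/40 |
|---|---|---|---|---|
| 20% | −0.9 | −2.4 | −0.4 | −1.2 |
| 40% | −1.7 | −4.6 | −0.8 | −2.3 |
| 80% | −2.7 | −7.4 | −1.4 | −3.7 |

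**Does the planned rate repair it?** With 25% late and constant hazard, simulated rates were 48.5, 111.1 and 348.9 per 100 patient-years against true values of 48.5, 111.1 and 349.9. Converted to 24-week risks they give 20.0%, 40.0% and 79.9%. With front-loaded onset (Weibull shape 0.5, true risk 80%, about 9 of 40 late), the crude figure is 76% and the rate converts to about 90%. Neither returns 80%.

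**Effect of delay.** The documents give no interval from the trigger to the lock or EoT visit. Under constant hazard, true risk 80% and 9.2 of 40 late at the trigger, the crude figure is 73% with no delay, 77% after 6 weeks, 79% after 12 and 80% after 24.

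**Contrast between arms.** If the true risks were 80% and 60%, with f = 0.25 and constant hazard, the crude figures would be 72.6% and 53.6%: a difference of 19.0 instead of 20 points.

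**The case against.** The strongest reply is that the SAP has seen the problem. SAP 7.8.1, to which the primary safety analysis refers, sets time at risk and rates per 100 patient-years beside N (%), expressly because exposure varies. SAP 7.8.1.2 stops time at risk at open-label start, last contact, death or lock. That stands: a reader might infer that unequal follow-up is ignored, and it is not. But the rate is a different quantity, and it translates to a 24-week risk only under a near-constant hazard. Protocol 3.2 says three months suffice to assess the most frequent AEs, and Protocol 1.2 places most hepatic events in the first three months, so a constant hazard is doubtful.

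Other points also stand, in part:

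- **Wording.** SAP 5.1 can be read as defining events in a period and not a 24-week risk. The week-24 label remains, so this argues for relabelling.
- **Size.** A reader might take 7 points as the expected bias. That needs undiminished accrual in a very rare disease, a data cut at the trigger itself and constant hazard. For scale, one standard error with about 27 nintedanib patients (two thirds of 40) at 73% is √(0.73 × 0.27/27) = 8.5 points.
- **DBL 2.** A reader might infer that the repeat analysis cannot help. EoT timing is announced only after PK adequacy is confirmed from DBL 1, so late entrants gain blinded weeks meanwhile. The repair is partial, because either route can still end Part A before week 24.
- **Comparison.** A reader might infer that one arm is favoured. Under 2:1 randomisation, late entry should not differ by arm; the absolute difference is only somewhat shrunk.
- **Withheld text.** The SAP contents list a further safety-endpoint section, 7.4.2.2, which is not public. It may already hold a suitable analysis.

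**Conclusion.** The point holds in limited form. The crude N (%) labelled as at week 24 is a downward-biased estimate of 24-week risk in both arms, because its denominator includes patients whose Part A was cut short. The supportable size is 0.4 to 7.4 points. That range rests on an assumed late share of 9% to 25%, true risks of 20% to 80%, uniform follow-up in late entrants, a cut at the trigger, and either constant or 12-week onset. It is probably smaller than sampling error, and it does not undermine the trial's safety conclusions. What remains after the SAP's mitigation is that the public text gives no week-24 cumulative incidence for any treatment-emergent AE. Since the remedy is cheap and does not depend on the hazard shape, the change is worth making.

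**What to change.** In SAP 7.4.1.2, add by arm the Kaplan-Meier cumulative incidence of first treatment-emergent AE at week 24 with 95% CI. Censor at the switch to open label, the end of double-blind time at risk or the data cut-off, using the rules of SAP 7.8.1.2. This gives the censoring instruction in SAP 7 something to act on. No new data or method is needed: SAP 7.8.1.3 already plans double-blind Kaplan-Meier curves for diarrhoea, bleeding and ILD.

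Keep the crude N (%) and the SOC/PT tables as descriptive, labelled as covering the double-blind period. Show the crude N (%) also for patients randomised at least 24 weeks before the cut-off. At DBL 2, count those weeks back from the date on which EoT visits or switches began, since Part A may have ended then. If SAP 7.4.2.2 already contains such an estimate, only the relabelling remains.

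While editing, correct the cross-reference: SAP 7.8.1 sends the reader to 7.8.1.1 for time at risk, but the derivation is in 7.8.1.2, whose title mentions only the whole trial.

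The cost is SAP wording, one extra table and a headline percentage with slightly wider uncertainty.

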8.1 TRIAL APPROVAL, PATIENT INFORMATION, INFORMED CONSENT

This trial will be initiated only after all required legal documentation has been reviewed and approved by the respective Institutional Review Board (IRB) / Independent Ethics Committee (IEC) and competent authority (CA) according to national and international regulations. The same applies for the implementation of changes introduced by amendments.

Prior to patient participation in the trial, written informed consent must be obtained from the patient’s legally accepted representative (and written informed assent must be obtained from the patient, where applicable) according to ICH-GCP and to the regulatory and legal requirements of the participating country. Each signature must be personally dated by each signatory and the informed consent (and assent where applicable) and any additional parental information form (and patient information form where applicable) retained by the investigator as part of the trial records. A signed copy of the informed consent (and assent where applicable) and any additional parental information (and patient information where applicable) must be given to the patient’s legally accepted representative (and the patient, where applicable).

The patient and the patient’s legally accepted representative must be given sufficient time to consider participation in the trial. The investigator or delegate obtains written consent of the patient’s legally accepted representative own free will with the informed consent form after confirming that the representative understands the contents. Moreover, where applicable, the investigator or delegate obtains written assent of the patient’s own free will with the informed

assent form after confirming that the patient understands the contents. The investigator or [REDACTED] delegate must sign (or place a seal on) and date the informed consent form (and the informed assent form where applicable). If a trial collaborator has given a supplementary explanation, the trial collaborator also signs (or places a seal on) and dates the informed consent (and the informed assent where applicable).

Re-consenting may become necessary when new relevant information becomes available and should be conducted according to the sponsor's instructions.

The consent and re-consenting process (together with the assent and re-assenting process where applicable) should be properly documented in the source documentation.

In order to ensure continued consent and assent, the investigator or [REDACTED] delegate will seek affirmation from the patient and patient's legally accepted representative as applicable about the continuation of the patient's participation in the trial during each visit. The fact that the patient appears for the regular visit as per protocol is enough affirmation in this aspect mean. The regular visit must be documented in the patient's medical records.

